Behavioural activation for depression (Beat-D) in adolescents with mild to moderate learning disabilities. A feasibility randomised controlled study of Beat-D versus treatment as usual

Sponsor:	University of Warwick				
Address:	University of Warwick, [name]				
Named Contact:					
Tel. No:					
E-mail:					

Chief Investigator	[name] CEDAR University of Warwick			
Funder and	Monash Warwick Alliance			
reference number				
REC number				
UKCRN number				
Version number	Version 1.4 16.03.2023			
and date				
Sponsor R&D				
number				

Signature Page for Investigators

Study Title: Behavioural activation (Beat-D) for depression in adolescents with mild to moderate learning disabilities. A feasibility randomised controlled study of Beat-D versus treatment as usual

I have read this protocol and agree to conduct this study in accordance with the stipulations of Good Clinical Practice (GCP) and all applicable regulatory requirements.

Chief Investigator

[name]

Signature

[name]

Date

16.01.2022

Chief Investigator:

[name]

CEDAR [name]

[contact]

E-mail: [contact]

Co-Investigators:

[name] Professor of Psychology

Centre for Educational Development Appraisal and Research (CEDAR) University of Warwick [name] UK

Email: [contact]

[name] Professor

Institute of Health and Wellbeing, University of Glasgow [name]

Email: [contact]

[name]

Centre for Educational Development Appraisal and Research (CEDAR) University of Warwick [name] UK [name] Research Assistant

Centre for Educational Development Appraisal and Research (CEDAR) University of Warwick [name] UK

Email: [contact]

Figure 1: Study flow chart

[figure not shown]

Table 1: Schedule of outcome measure assessments during trial (see section 10 for further details on outcome measures)

	Demographic & health questionnaire	Self-report depressive symptoms	Proxy- report depressive symptoms	Activity questions	Carer efficacy questionnaire	Behaviour and emotional problems	Quality of life and well- being measures	Qualitative interview
Baseline	X	Х	X	Х	X	Х	X	
Time 2 (≈ 4 months from randomisation)		X	X	X	Х	X	Х	X (sub sample)

1.0 Study Summary

Adolescents with learning disability (LD) face significant mental health inequalities. Children and adolescents with LD are 4-5 times more likely to have mental health problems compared to children and adolescents without LD. The inequalities include a lack of tested effective treatments. We aim to address this neglected area of mental health research, establishing a platform internationally for developing/adapting and evaluating psychological treatments. A working method will be developed via a feasibility study of a psychological treatment for depression in adolescents with LD.

Depression is the third leading contributor to the global burden of disease, and the World Health Organization predicts it will be the second leading contributor to global burden by 2020. Young people with LD are 1.7 times more likely to experience depression than other young people. Depression causes avoidable human suffering for people with ID, their families and local communities.

Psychological therapies, such as cognitive behavioural therapy (CBT), are recommended as the best treatment for most people with depression. Improving access to psychological therapies is an NHS priority. However, psychological therapies require good verbal communication. Studies have shown that people with LD do not have the communication skills to participate in most available psychological therapies.

Clinical guidelines recommend the provision of individual psychological therapy for children and adolescents with moderate-severe depression. However, recent international reviews have established that there is no quality evidence for psychological therapies for children and adolescents with ID. To date, studies of the treatment of depression in children and adolescents have not included children with LD.

Behavioural Activation is a psychological therapy that has been shown to be as effective as CBT. The advantage for people with LD is that Behavioural Activation is less dependent on verbal communication. Behavioural Activation gets people with depression involved in positive activities and helps them engage in everyday tasks which people with depression avoid. We have shown that Behavioural Activation is effective for adults with mild/moderate LD (Beat-It-A). The proposed study will examine the effectiveness of the Behavioural Activation intervention that has been slightly adapted for adolescents with mild to moderate LD and depression (Beat-D).

In the proposed study, half the participants will take part in the Beat-D (behavioural 16.03.2023 Version 1.4 6

activation) treatment, and half will receive usual NHS treatment. People who choose to take part will be involved for a maximum of six months. The study will take place in Birmingham. We would like to find out: i) if we can recruit participants to the study, ii) if we can collect the outcome measures iii) what people think about the treatment and research study design.

Our team is made up of researchers with expertise in working with people with LD, experts on clinical therapeutic interventions, and experts in using statistics in research. In the study centre, we have strong links with the NHS and specialist learning disabilities service.

2.0 Background

2.1 The health need

A significant proportion of the UK population has LD. Approximately 2% of adults and 3.5% of children have an intelligence quotient <70, although this figure may be rising due to increasing life expectancy and birth rate (e.g. improving survival of very low birth weight babies, increasing maternal age) ^{1&2}. Individuals with LD experience health inequalities, with needs not well met by the NHS ³⁻⁵. They have much higher levels of mental ill-health than the general population, with a point prevalence of 40% for adults ⁶. This is a burden at the individual, family and societal level, including a cost burden. For example, England spends £3 billion per annum on specialist support for persons with LD, with the prevalence of their poorly addressed mental health needs contributing to costs⁷. This is 50% of the equivalent amount spent on mental ill-health in the general population ⁸, despite being provided for only 2% of the population.

Depression is a major public health challenge. Unipolar depression alone is the third leading contributor to the global burden of disease and its prevalence is expected to rise ⁹. Depression is highly prevalent amongst adolescents with LD and contributes to human misery, as well as cost of daily care and support.

2.2 Psychosocial interventions

Considerable work has been carried out to develop and study the efficacy of psychosocial interventions for depression in the general population. Such evidence is missing for people with LD. There is, therefore, a need to redress this inequity by identifying effective therapies for adolescents with LD. Recent efforts have focused on the adaptation of cognitive behavioural treatment (CBT) models for use with individuals with LD ¹⁰, but the efficacy of CBT has yet to be rigorously tested. Furthermore, studies have shown that CBT is not

accessible for the majority of individuals with LD, due to the cognitive and communicative demands⁵.

2.3 Behavioural Activation

A meta-analysis of studies with the general population found that behavioural activation is as effective as CBT in the management of depression ¹¹. Models of behavioural activation interventions aim to increase overt behaviours that are likely to bring the individual into contact with positive environmental contingencies, with a corresponding improvement in mood, thoughts, and overall well-being. Because behavioural activation does not focus on monitoring the relationship between thoughts and other symptoms, the intervention is less reliant than CBT on verbal communication to access emotions and thoughts. Therefore, for adolescents with LD, behavioural activation treatment may be more accessible and effective in the management of depression.

Models of behavioural activation treatments¹²⁻¹³ have evolved from earlier behavioural approaches and take greater account of the context of an individual's life. They have a focus on understanding the function of an individual's behaviour. Establishing the function of behaviour for the individual is crucial because the aim is not merely to increase activity, but to ensure that activities are purposeful and motivating for the individual.

Taking account of the context of a person's life is especially important when working with marginalised and more dependent individuals. People with LD may have limited opportunities to participate in a range of occupational or social activities ¹⁴. By definition, they have problems with adaptive behaviour (day-to-day social, communication, and life skills), in addition to cognitive impairments ¹⁵. Therefore, they are likely to rely on a degree of support to take advantage of opportunities for activity that do arise. Hence, the first step to increasing the levels of activity would be to ensure that the necessary opportunities and supports are in place. For a behavioural activation treatment to have ecological validity, in that it makes sense in the everyday context of the individuals' lives, it is necessary to work alongside families or paid carers who are already providing help. As a result, the Beat-It-A treatment adapted for use by adults with LD works with dyads of individuals and their carers to develop a structured programme of activities and strategies for increasing motivation ¹⁶. This systemic approach is also designed to improve the generalisation and maintenance of the treatment's impact. This approach has been further adapted for use with adolescents with LD and depression.

2.4 Beat-D clinical trial

For this feasibility RCT, the Beat-It-A treatment manual has been carefully tailored to take account the needs of adolescents with mild to moderate LD. The adapted treatment manual has been named ''Beat-D''.

This is a randomised controlled trial of Beat-D for depressive symptoms experienced by adults with mild-moderate LD demonstrated positive change on depressive symptoms at 4 and 12 months post-treatment ¹⁶, with strong effect sizes on the Glasgow Depression Scale¹⁷ and carer report using the Intellectual Disabilities Depression Scale¹⁸.

3.0 Study objectives

3.1 Primary objective

To comprehensively evaluate the feasibility of a treatment trial for depression in adolescents with mild to moderate LD.

3.2 Secondary objectives

- 1. How acceptable is the treatment to the adolescents with LD, their parents/carers, and therapists? Do therapists feel the therapeutic processes were appropriate for adolescents and their parents/carers?
- 2. What is the rate of recruitment of adolescents with depression and mild-moderate LD to the study over a 10-month period?
- 3. What is the retention rate of the recruited adolescents with LD six-months post-randomisation?
- 4. Which outcome measures (potential primary and secondary outcome measures) have greatest utility to detect meaningful change in the participants with LD, and their parents/carers?
- 5. Are adverse events associated with the treatment in this study population?
- 6. What are the reasons for study non-completion?
- 7. Is behavioural activation delivered with fidelity to the manual/model, and what is the adherence of participants to the treatment?
- 8. What is treatment as usual for adolescents with LD and depression?

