10.0 Study Outcomes

10.1 Measures/assessment instruments

As shown in Figure 1, outcome measure data will be collected at two time points:

- Baseline
- Time 1 four months post-randomisation (post intervention)

Data collection interviews should take place as close to the scheduled data collection point as possible and always within the period of between two weeks before and four weeks after the due date (based on date of randomisation).

Outcome measures for the feasibility study include:

- 1. Depressive and anxiety symptoms
- 2. Behavioural Activation and coping ability
- 3. Participant activity levels
- 4. Quality of life
- 5. Carer efficacy
- 6. Service use (information about service supports and treatments)

An outline of data collected at the two time points is shown in Table 2, below. Research interviews will take place in the home environment of participants. If participants prefer, these interviews will take place in appropriate clinical, provider organisation or charity premises. In addition to the assessments listed in Table 2, a purpose specific questionnaire to gather demographic and health data about participants will be completed at baseline only. This will include questions about the participants' expectations of therapy. This questionnaire was used in the initial Beat-It-A (for adults) clinical trial and takes 20 minutes to complete.

Carers will also be given the option to complete assessments with the researcher by phone if it proves to be more convenient for them or difficult to arrange a time to meet face to face.

Table 2: Outcome measure assessments

Outcome	Measures
Depressive symptoms	Glasgow Depression Scale for Intellectual Disabilities (20 items: 10 minutes)
	Glasgow Depression Scale for Intellectual Disabilities – Caregivers Supplement (16 items: 10 minutes)
Behavioural Activation	BADS (8 items: 10 minutes)
Anxiety symptoms	Glasgow Anxiety Scale for Intellectual Disabilities (27 items: 10 minutes)
	Spence Children's Anxiety Scale – Parent Report (45 items: 15 minutes)
Carer Self-efficacy	Emotional Difficulties Self-Efficacy Scale (10 items: 5minutes)
Quality of life	EQ-5D-Y Proxy version (5 dimensions: 5 minutes)
	EQ-5D-Y Interviewer Administered version (5 dimensions: 10 minutes)
Health economics	Client Service Receipt Inventory (30 items: 10 minutes)

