12.0 Statistical considerations

12.1 Randomisation

Participants will be allocated to one of two study groups using random permuted blocks. The randomisation lists will be developed by the trial statistician, who will not be involved in recruitment, data collection, or statistical analysis. The final lists will be passed to the study coordinator, who will save them in a restricted folder (i.e. not accessible by those who are to remain blind to allocation for the duration of the study period).

After obtaining informed consent and the collection of baseline information, participants will be allocated to one of the two study groups.

The research assistant will e-mail the study coordinator with the participant's screening number, age, and gender (for verification). The study coordinator will access the list corresponding to the participant's centre and assign the next available allocation to the participant. The allocation will not be revealed to the research assistant. Following this, the study coordinator will contact the clinicians to arrange subsequent study visits.

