14.3 End of study

The end of the study is defined as the last participant's final visit from relevant research staff and will be reported to the sponsor, research ethics committee and NHS R&D.

Once the final report has been approved by the study funder a copy will be sent to the sponsor and NHS R&D offices. A summary report of the study will be provided to the research ethics committee within one year of the end of the study.

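### Secondary objective 3 asks for retention at six months after randomisation, but the only scheduled follow-up is at four months and its window closes about 33 days before six months

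*Protocol*

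**What the plan says.** Four parts of the protocol bear on this.

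- **Section 3.2, secondary objective 3**, sets the time point for retention: "What is the retention rate of the recruited adolescents with LD six-months post-randomisation"?
- **Section 10.1** states that "outcome measure data will be collected at two time points". These are baseline and "Time 1 four months post-randomisation (post intervention"). Interviews must fall "always within the period of between two weeks before and four weeks after the due date (based on date of randomisation").
- **Table 1** agrees. It has a baseline row and one other, "Time 2 (≈ 4 months from randomisation"), and the qualitative interview for a subsample sits in that second row.
- **Section 1.0** says: "People who choose to take part will be involved for a maximum of six months". It does not say whether that period starts at consent, at baseline or at randomisation.

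Two further statements matter for the reading. Section 12.1 puts consent and baseline before randomisation: "After obtaining informed consent and the collection of baseline information, participants will be allocated to one of the two study groups". Section 14.3 fixes the close of the study: "The end of the study is defined as the last participant's final visit from relevant research staff".

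**The concern.** The objective and the schedule both count from randomisation, so a difference in starting point cannot reconcile them. One names six months. The other provides data at four months, with a window that does not stretch to six.

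The primary objective is to evaluate the feasibility of a treatment trial. Retention, with recruitment, is one of the few numerical quantities by which that will be judged, and it is a natural input to the attrition allowance of the next trial. As written, the objective may go unanswered, or the four-month figure may be reported under a six-month label. Status that nobody checks at six months is also hard to recover afterwards.

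**Working it through.** The protocol gives no closing time for the window in months, so there is no stated figure to reproduce. The check is date arithmetic.

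**Inputs**
- Time point for retention: 6 months after randomisation (section 3.2).
- Only follow-up: 4 months after randomisation (section 10.1, Table 1).
- Window: 14 days before to 28 days after the due date (section 10.1).
- Month length: 365.25/12 = 30.44 days (assumption, varied below).

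**Window**
- Opens: 4 − 14/30.44 = 3.54 months.
- Closes: 4 + 28/30.44 = 4.92 months.
- In weeks, 4 months = 4 × 30.44/7 = 17.39, so the window closes at 17.39 + 4 = 21.39 weeks.
- Six months = 6 × 30.44/7 = 26.09 weeks.
- Gap: 26.09 − 21.39 = 4.70 weeks, or 1.08 months (about 33 days).

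**Sensitivity to month length**

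| Month length (days) | Window closes (months) | Gap to six months (days) |
|---|---|---|
| 28 | 5.00 | 28 |
| 30 | 4.93 | 32 |
| 30.44 | 4.92 | 33 |
| 31 | 4.90 | 34 |

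With actual calendar dates, for every randomisation day in one year, the gap is 32 to 34 days. On every convention it is at least 28 days. An outcome interview held at six months would fall outside the protocol's own window.

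**Is six-month status obtained in any other way?**
- Section 7.0 lets participants withdraw at any time, but it sets no six-month check and does not define retention.
- Section 8.1 has treatment spanning about four months, so therapist contact does not clearly reach six.
- The limit in section 1.0 is an upper bound. If it runs from consent, six months after randomisation lies beyond a participant's involvement, because consent and baseline come first. If it runs from randomisation, six months is the outer edge, still with no contact attached.
- Figure 1 is not shown in the text at hand, but section 10.1 cites it for the same two time points.

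**Who could be cut off by the end of the study?** Assume that the last research visit is the four-month assessment of the last participant randomised. The study then closes between 3.54 and 4.92 months after that randomisation. Anyone randomised less than 6 − 4.92 = 1.08 months before the last participant cannot reach six months while the study is open. Anyone randomised more than 6 − 3.54 = 2.46 months before does reach it. In between, it depends on when the last visit falls.

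**Effect of mislabelling.** If retention has the same definition at both times and lost participants do not return, it cannot rise between four and six months. A four-month figure is then equal to or above the six-month one. With the planned 20 participants, each loss in between would move the overall rate by 1/20 = 5 percentage points. The protocol gives no attrition figure, so the number of such losses is unknown and may be zero.

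**The case against.** The strongest counter-argument is that the protocol never defines retention as completing an outcome assessment. Retention can also mean not having withdrawn. Withdrawal is allowed at any time, involvement may last up to six months, and objective 2 in section 3.2 has recruitment running over 10 months. Many participants would therefore pass six months while the study is open, and a withdrawal could be recorded. That stands in part. A reader might infer that six-month retention cannot be measured at all, or that the later weeks go unobserved for every participant. The documents do not support that: passive logging is possible for those randomised early, and the end-of-study rule cuts off only those randomised late. What remains is that the protocol describes no such logging, and logging would miss anyone who simply drifts away.

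A reader might also infer that retention will be overstated. That holds only if a four-month figure carries a six-month label and someone is lost in between.

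It can be added that this is one time label in one of eight secondary objectives, and that neither the sample size, the randomisation, the safety reporting nor the analysis in section 12.2 depends on it. That is correct and bears on severity.

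Finally, a statistical analysis plan, not seen here, might define retention. It could not supply a contact that the protocol does not schedule, and both the objective and the visit schedule are fixed in the protocol.

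**Conclusion.** The point holds as an internal inconsistency: six-month retention is named as an objective, and the schedule does not support it. The only follow-up closes at about 4.9 months, leaving a gap of about 33 days (28 to 34 on the conventions tried). The text provides no contact or status check to fill it.

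It is a moderate matter in a secondary feasibility objective and does not threaten the trial. The gap rests only on the stated times and window. The consequence for late-randomised participants also assumes that the final research visit is the four-month assessment, which section 14.3 implies but does not say. The direction of any mislabelling error rests on retention being defined in the same way at both times.

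**What to change.** Reconcile section 3.2 (objective 3), section 10.1, Table 1 and the participation limit in section 1.0.

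**Simplest route.** Restate objective 3 along these lines: *What proportion of randomised adolescents complete the four-month post-randomisation assessment?* Count participants assessed after the window as retained, and report separately how many assessments fell within it. Counting only in-window completers would mix lateness with attrition. This costs one line and no extra data collection. The claim becomes four-month retention instead of six-month, and anyone planning a trial with longer follow-up would have to allow for that.

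**If six-month retention is really wanted.** State how and when six-month status will be ascertained, for example by a brief status check, and what counts as retained. Make section 1.0 (start and length of involvement) and section 14.3 (end of study) consistent with it. The cost is one short contact per participant and possibly a later close of the study. The four-month assessment can stay where it is.

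While editing, give the follow-up one name: Table 1 calls it Time 2 and section 10.1 calls it Time 1.

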4.0 Study design

The proposed study is a single-centre, single-blind, feasibility randomised controlled trial (RCT) of Beat-D compared to treatment as usual, plus a qualitative investigation of adolescents', carers', and therapists' perspectives on the treatment. The design of the study is illustrated in Figure 1, and the schedule of research assessments outlined in Table 1. The researchers collecting the outcome data will be blinded to which group participants have been allocated.

